6.1.2.1 Dose Limiting Toxicity

A dose limiting toxicity is defined as the occurrence of any of the following:

- A Grade ≥ 3 toxicity that is probably or possibly related to the investigational product, defined according to the Common Terminology Criteria for Adverse Events (CTCAE) Version 5.0.
- A confirmed serum phosphate level of ≥ 8 mg/dL for pediatric subjects, or ≥ 6.5 mg/dL for adult subjects (defined as hyperphosphatemia) at any time after dosing.

If a subject experiences a dose limiting toxicity, the planned dosing for that subject will be evaluated by the Investigators. The outcome of this investigation will determine the subject's continuation or withdrawal from the study, as described in the Section Discontinuation of Study Intervention.

The following laboratory abnormalities will necessitate discontinuation of study drug:

- Documented decline in estimated glomerular filtration rate (eGFR) to <30 mL/min/1.73m² for pediatric patients, or <30 mL/min for adults

6.1.2.2 Dose Modifications

See the Section **6.1.2, Dosing and Administration** for dose modification criteria in response to serum phosphate.

6.1.2.3 Drug Administration

For the initial NIH visit, the NIH pharmacy will dispense the burosumab vial(s) directly to the NIH Patient Care Unit responsible for administering the drug. Subjects and/or caregivers will receive injection teaching from a study team member at the initial NIH visit, which will include verbal and written instructions (see Appendix 2). The subject and/or caregiver's proficiency will be assessed by observation of injection of normal saline into a teaching model device. All home injections will be supervised by the study team via telehealth appointment. A study team member will travel to home sites for the second dose to observe patient home administration and verify proficiency and injection teaching and inspection of burosumab storage and handling at home.

Subjects will receive an additional proficiency check and injection teaching at Week 24. If in the opinion of the PI, caregivers are not suitably proficient to administer injections, a study team member who is a licensed medical professional will travel to subject's home location and administer the medication to prevent interruption of therapy. Subjects may also return to NIH for injections. Federal, state and local policies, procedures and regulations dictate practice related to the safe transportation of the medication and handling of waste in/from the subjects' homes. For

subjects receiving home injections, the NIH Pharmacy will ship the study drug and supplies to the subject's home. The drug will be shipped on ice, and subjects will be instructed to store the drug in a refrigerator until time of use. Subjects will also be instructed on safe disposal of needles after use.

6.2 Preparation/Handling/Storage/Accountability

6.2.1 Acquisition and Accountability

The site research pharmacist or delegated personnel will maintain an accurate record of the receipt of the burosumab (shipped by Kyowa Kirin), including the date and quantity received. In addition, an accurate drug disposition record will be kept that specifies the amount to be administered to each participant, the date of dispensation, and any amount returned. Subjects will be instructed to return any unused drug during the final study visit. This inventory record must be available for inspection at any time. The NIH pharmacy in collaboration with the PI is responsible for keeping accurate records of the amount of drug dispensed, returned and remaining at the conclusion of the study.

6.2.2 Formulation, Appearance, Packaging, and Labeling

Burosumab will be provided as a sterile, preservative-free, clear to slightly opalescent and colorless to pale brown-yellow solution. Single-dose vials will be dispensed in 10 mg/mL, 20 mg/mL, and/or 30 mg/mL concentrations. Burosumab is manufactured by Kyowa Kirin, Inc, Bedminster, NJ, U.S. License No. 2077

6.2.3 Product Storage and Stability

Kyowa Kirin, Inc will provide drug supplies to the study center. Burosumab vials will be stored under refrigerated conditions at 36°F to 46°F (2°C to 8°C). Reuse of vials is not permitted after the seal is broken. The expiration date is labeled and use of burosumab after the expiration date is not permitted.

6.2.4 Preparation

Not applicable

6.3 Measures to Minimize Bias: Randomization and Blinding

Not applicable

6.4 Study Intervention Compliance

Outpatient burosumab administration will be directly observed and documented by a member of the study team via telehealth assessment. Participants will return any unused burosumab vials at their next designated NIH visit, which will be reviewed for accountability and an estimate of compliance.

6.5 Concomitant Therapy

At screening and enrollment, the study staff at NIH will question each subject specifically on the use of all concomitant medications and record the medication, dosage, and duration of use in the appropriate CRF. In general, upon admission and throughout the study, site staff will monitor, record, and administer all concomitant medications during the NIH stay. Investigators may

prescribe any concomitant medications or treatments deemed necessary to provide adequate supportive care.

All subjects who are receiving conventional therapy at screening will be instructed to stop taking pharmacologic vitamin D metabolites or analogs (e.g., calcitriol, alfacalcidiol, doxercalciferol, and paricalcitol) and oral phosphate supplements on Week -2. These medications will remain prohibited throughout the conduct of the study. Any subject who resumes or requires the use of any of these medications will be discontinued from the study. Patient safety during this washout time period will be monitored and adverse events will be reported as described in Section [10.5](#).

7 STUDY INTERVENTION DISCONTINUATION AND PARTICIPANT DISCONTINUATION/WITHDRAWAL

7.1 Study Intervention Discontinuation

Discontinuation from burosomab does not mean discontinuation from the study, and remaining study procedures should be completed as indicated by the study protocol. If a clinically significant finding is identified after enrollment (including, but not limited to changes from baseline), the investigator or qualified designee will determine if any change in participant management is needed. Any new clinically relevant finding will be reported as an adverse event (AE).

The data to be collected at the time of study intervention discontinuation for subjects who prematurely discontinue burosomab will include the following, as described in detail in Section [10.8](#):

- NIH lab tests
- Physical Medicine and Rehabilitation evaluation
- Administration of questionnaires for patient-reported outcomes
- Activities of Daily Living questionnaires

Subjects are free to withdraw from participation in the study at any time upon request.

An investigator may discontinue or withdraw a subject from the study for the following reasons:

- Completion of study intervention
- If any clinical adverse event (AE), laboratory abnormality, or other medical condition or situation occurs such that continued participation in the study would not be in the best interest of the participant
- Investigator discretion
- Positive pregnancy test
- Subject unable to receive burosomab for 12 weeks

7.2 Participant Discontinuation/Withdrawal from the Study

If subjects discontinue participation or are terminated early from the study, they should be converted back to their outpatient conventional therapy regimen of oral phosphate and active vitamin D analogs. Subjects will be instructed to undergo outpatient laboratory testing of their blood phosphate within 1-7 days of discontinuing study medication and to have those results sent to NIH investigators for review. A telephone contact should be arranged for the investigative staff to review the lab results and advise on optimizing their outpatient clinical management.

All subjects who received burosumab and terminated early from the study, regardless of cause, should undergo a 30-day (\pm 7 days) follow-up telephone call after the last dose of burosumab. The reason for early termination from the study will be reflected in the CRF. If a subject terminates early from the study because of an AE, the PI/study staff must record the AE as the reason for discontinuation.

7.3 Lost to Follow-up

A subject will be considered lost to follow-up if he or she missed at least 3 documented phone calls, followed by no response after a registered letter to the participant's last known mailing address is received.

The following actions must be taken if a subject fails to return to the clinic for a required study visit:

- The site will attempt to contact the subject and reschedule the missed visit and counsel the subject on the importance of maintaining the assigned visit schedule and ascertain if the subject wishes to and/or should continue in the study.
- Before a subject is deemed lost to follow-up, the investigator or designee will make every effort to regain contact with the subject (where possible, 3 telephone calls and, if necessary, a certified letter to the subject's last known mailing address or local equivalent methods). These contact attempts should be documented in the subject's medical record or study file.
- Should the subject continue to be unreachable, they will be considered to have withdrawn from the study with a primary reason of lost to follow-up.

8 STUDY ASSESSMENTS AND PROCEDURES

8.1 Screening Procedures

Screening for this protocol will be done under protocol 98-D-0145 (NCT00001727).

Screening process:

New subjects participating in protocol 98-D-0145 will have an evaluation as part of that study to confirm the diagnosis of FD/MAS, obtain routine and bone-specific blood work (per that protocol) and to characterize the extent of disease. Subjects diagnosed with FD/MAS will be offered enrollment into the burosumab protocol.

Subjects already enrolled into protocol 98-D-0145 with confirmed FD/MAS and hypophosphatemia will be offered enrollment into the burosumab protocol. If the subject is interested in enrollment and hasn't had a recent visit for the 98-D-0145 protocol, the subject will be asked to come back to NIH for an evaluation to obtain an updated history, physical exam and blood work as part of protocol 98-D-0145.

Identifiable subject data will be shared between protocol 98-D-0145 and this study. The data captured on 98-D-0145 that will be shared and used to demonstrate eligibility for this study includes the diagnosis of FD/MAS, results of laboratory, imaging and other measures that define and characterize the scope of the disease. The outcome results of the following procedures/tests from the protocol 98-D-0145 will be evaluated as screening tests to determine eligibility into the burosumab protocol: imaging studies, serum phosphate, and serum FGF23 levels.

Subjects who have lab work returned that fulfill all eligibility and no exclusion criteria will be scheduled for an NIH visit. Visits will be conducted in the NIH Clinical Center in the inpatient, day hospital, or clinic settings as appropriate. If the subject is eligible for the burosomab protocol based on the screening tests performed within protocol 98-D-0145 and is interested, the protocol will be explained to them and the consent process implemented. If willing to participate in the study, the subject or LAR will be asked to sign informed consent. Consent for participation in the burosomab protocol will be obtained before any study specific procedures are performed. If a subject declines to participate in the burosomab protocol, they have the option to remain in protocol 98-D-0145.

8.2 Study Evaluations & Procedures

All subjects who are currently receiving active vitamin D analogs and oral phosphate supplements will be asked to discontinue these medications at week -2 prior to baseline visit.

The following procedures and imaging assessments will occur according to Section **1.3, Schedule of Activities (SoA)** in order to support determination of efficacy, as per the primary and secondary objectives:

Serum phosphate concentrations: Samples will be collected and tests performed at the NIH Clinical Center. Between NIH visits, samples will be collected and evaluated at outpatient laboratories near subjects' homes.

Physical Medicine and Rehabilitation evaluation: 9-minute walk/run test (ambulatory patients), range-of-motion testing, activity of daily living assessment, and manual muscle testing. Standardized and validated measures of functional status used routinely by the Clinical Center Rehabilitation Department will be obtained.

Administration of questionnaires for patient-reported outcomes

Patients will be asked to complete questionnaires to assess change from baseline to 48 weeks in patient reported outcomes measures. Adults will be asked to complete the patient-reported 36-item Short Form Health Survey (SF-36). Pediatric patients age 5-18 will be asked to complete the SF-10™ Child Health Survey. The following PROMIS questionnaires will be administered:

- PROMIS Pain Intensity: Pediatric and Parent Proxy version 1.0 (children), Adult version 2.0 (adults)
- PROMIS Pain Interference: Pediatric and Parent Proxy v 2.0 (children), Adult v 1.1 (adults)
- PROMIS Mobility: Pediatric and Parent Proxy version 2.0 (children), Adult Mobility Lower Extremity v 1.0 (adults)
- PROMIS Fatigue: Pediatric and Parent Proxy v 2.0 (children), Adult FACIT 13a v1.0 (adults)

Pediatric questionnaires will be administered to subjects age 8-17 years, and Parent Proxy questionnaires will be administered to caregivers of subjects age 7 years and younger. Parent Proxy questionnaires may be administered to caregivers of subjects age 8 years and older at the discretion of the PI if considered developmentally appropriate.

8.2.1 Activities of Daily Living Questions

Patients and/or caregivers will be asked during the Baseline clinical visit to provide a list of 3 activities of daily living that are affected by FD skeletal features at home or school/work (e.g., mobility, climbing stairs, dressing, playing with peers, catching a bus, etc) and to estimate the extent of impact upon their activity level (see Appendices). These activities will then be reassessed at Week 24 and Week 48 for the level of change since Baseline on the extent of the impact upon these 3 activities.

8.2.2 Biospecimen Evaluations

NIH lab tests: The following laboratory evaluations will be obtained and performed at the NIH Clinical Center according to Section **1.3, Schedule of Activities (SoA)**. For some tests, the NIH Clinical Center may contract and send samples to specialized outside laboratory facilities.

- Serum sodium, potassium, chloride, bicarbonate, glucose, blood urea nitrogen, creatinine, albumin, total protein, calcium, magnesium, phosphate, parathyroid hormone, 25-hydroxyvitamin D, 1,25-dihydroxyvitamin D, aspartate aminotransferase, alanine aminotransferase, total bilirubin, alkaline phosphatase, bone-specific alkaline phosphatase, osteocalcin, procollagen type 1 N-terminal propeptide, Beta-CrossLaps C-telopeptides, intact FGF23, C-terminal FGF23, and TmP/GFR.
- 24-hour urinary calcium, creatinine, phosphate.

Outpatient lab tests: The following laboratory evaluations will be obtained at outside laboratory facilities close to subjects' homes:

- Serum calcium, phosphate, creatinine, alkaline phosphatase.
- Random urine calcium, creatinine, phosphate.

The following laboratory evaluations will be performed at BioAgilytix Labs, LLC and Toray Research Center, Inc, specialty lab services that have been previously contracted by Ultradex:

- Anti-burosomab antibodies, and burosomab concentration. If anti-burosomab antibodies are detected, these samples will subsequently be evaluated for the presence of neutralizing antibodies.

Clinical Safety lab tests:

- Serum sodium, potassium, chloride, bicarbonate, glucose, blood urea nitrogen, creatinine, calcium, phosphate, aspartate aminotransferase, alanine aminotransferase, total bilirubin, alkaline phosphatase
- Random urine calcium, creatinine, phosphate
- Anti-burosomab antibodies, neutralizing antibodies (in samples with detectable anti-burosomab antibodies), and burosomab concentration

The total amount of blood to be drawn over this study is 203 mL. The maximum amount drawn over an 8-week period is 67.5 mL. This is below the maximum safety threshold for adults of 550 mL over an 8-week period determined by the NIH Clinical Center. Based on the minimum weight requirement for this study (7.5 kg), this corresponds to a maximum potential blood draw volume of 9 mL/kg over an 8-week period for pediatric patients. This is below the maximum safety threshold of 9.5 mL/kg over an 8-week period determined by the NIH Clinical Center.

Abbreviated Title: Burosomab for FD

Version Date: 02/20/2024

The maximum amount of blood drawn in a single day will not exceed 5 mL/kg for pediatric subjects. Bone tissue from a minimally invasive biopsy pre- and post-treatment will be obtained in adult subjects at the NIH. Tissue will be limited to 1-4 cores from standard bone biopsy needles.

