1.3 Schedule of Activities (SoA)

Abbreviated Title: Burosumab for FD

Version Date: 02/20/2024

Procedures	Week 26	Week 28	Week 30	Week 32	Week 34	Week 36	Week 38	Week 40	Week 42	Week 44	Week 46	Week 48 Visit (NIH CC) ³	Week 50
Informed consent	-	-	-	-	-	-	-	-	-	-	-	-	-
Demographics	-	-	-	-	-	-	-	-	-	-	-	-	-
Medical history	-	-	-	-	-	-	-	-	-	-	-	X	-
Physical exam (including height, arm span, and weight)	-	-	-	-	-	-	-	-	-	-	-	X	-
Vital signs	-	-	-	-	-	-	-	-	-	-	-	X	-
Injection teaching	-	-	-	-	-	-	-	-	-	-	-	-	-
Functional parameters ⁴	-	-	-	-	-	-	-	-	-	-	-	X	-
NIH lab tests ⁵	-	-	-	-	-	-	-	-	-	-	-	X	-
Outpatient lab tests ⁶	-	X	-	X	-	X	-	X	-	X	-	-	-
Pregnancy test ⁷	-	X	-	X	-	X	-	X	-	X	-	X	-
Bone biopsy ⁸	-	-	-	-	-	-	-	-	-	-	-	X	-
Imaging assessment ⁹	-	-	-	-	-	-	-	-	-	-	-	X	-
Patient reported outcomes ¹⁰	-	-	-	-	-	-	-	-	-	-	-	X	-
Burosumab administration (pediatric subjects) ¹¹	X	X	X	X	X	X	X	X	X	X	X	-	-
Burosumab administration (adult subjects) ¹¹	-	X	-	X	-	X	-	X	-	X	-	-	-
Study close-out teleconference (pediatric subjects) ¹²												X	
Adverse event review and evaluation ¹²													

¹ Informed consent will be obtained by telephone or in person prior to the baseline visit.

² Subjects receiving supplemental phosphate, active vitamin D metabolites, or current burosumab treatment will discontinue these medications for 2 weeks prior to screening.

³ Visits will be conducted in the NIH Clinical Center in the inpatient, day hospital, or clinic settings as appropriate. All visits will occur within a window of +/- 5 days from the planned timepoint.

⁴ Muscle strength, range-of-motion, 9-minute walk test.

Abbreviated Title: Burosumab for FD

Version Date: 02/20/2024

⁵ Serum sodium, potassium, chloride, bicarbonate, glucose, blood urea nitrogen, creatinine, albumin, total protein, calcium, magnesium, phosphate, parathyroid hormone, 25-hydroxyvitamin D, 1,25-dihydroxyvitamin D, aspartate aminotransferase, alanine aminotransferase, total bilirubin, alkaline phosphatase, osteocalcin, procollagen type 1 N-terminal propeptide, Beta-CrossLaps C-telopeptides, intact FGF23 (baseline visit only), C-terminal FGF23 (baseline visit only), research blood, anti-drug antibodies, neutralizing antibodies (in samples testing positive for neutralizing antibodies only), and burosumab concentration. 24-hour urinary calcium, creatinine, phosphate (toilet trained subjects), random urinary calcium, creatinine, phosphate (non-toilet trained subjects), and TmP/GFR.

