⁶ Serum calcium, phosphate, creatinine, and alkaline phosphatase. Random urine calcium, creatinine, and phosphate. Urine pregnancy test (girls and women of childbearing potential only). Outpatient labs will be obtained 3 +/- 2 days and reviewed prior to burosumab administration. Subsequent elements on the Schedule of Events will be dictated by the timing of the previous injection.

⁷ To be performed in girls and women of childbearing potential only. Female subjects of child-bearing potential must be non-pregnant and non-nursing. Additional pregnancy tests will be performed at any visit in which pregnancy status is in question. A serum pregnancy test will be performed in the event of a positive or equivocal urine pregnancy test result or can be performed if pregnancy test by urine is not feasible.

⁸ To be performed only in adult subjects with capacity to consent.

⁹ ¹⁸Sodium fluoride-PET/CT scan, skeletal survey, renal ultrasound. Will accept outside or internal imaging for ¹⁸Sodium fluoride-PET/CT scan, and/or skeletal survey as baseline study imaging if obtained within 6 months prior to Week 0/Baseline visit, as a means of reducing unnecessary repeated exposure to radiation

¹⁰ SF36 (adults), SF10 (children), PROMIS Pain Intensity (Pediatric and Parent Proxy version 1.0, Adult version 2.0), PROMIS Pain Interference (Pediatric and Parent Proxy v 2.0, Adult v 1.1), PROMIS Mobility (Pediatric and Parent Proxy version 2.0, Adult Mobility Lower Extremity v 1.0), PROMIS Fatigue (Pediatric and Parent Proxy v 2.0, Adult FACIT 13a v1.0), Activities of Daily Living Questionnaire (adults and children).

¹¹ Burosumab is administered every 2 weeks in children age <18 years, and every 4 weeks in adults age \geq 18 years. The initial dose will be administered at the NIH CC, and subsequent doses will be self/caregiver administered under the observation of the study team. If the target range is not reached for patients >18 year and older, dosing may be administered at every 2-week dosing intervals at the discretion of the PI.

¹² Final adverse event review will be performed 4 weeks +/- 5 days after the final dose: at the 48 week NIH CC visit for adult subjects, and at a teleconference at 50 weeks for pediatric subjects, or adult subjects who have been on every 2-week dosing interval.

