5 STUDY POPULATION

5.1 Inclusion Criteria

In order to be eligible to participate in this study, an individual must meet all of the following criteria:

1. Confirmed diagnosis of fibrous dysplasia
2. Serum phosphate <10th percentile for age and sex, AND intact serum FGF23 ≥ 30 pg/mL[16]
3. Age ≥ 1 year
4. Provision of signed and dated informed consent/assent form

5. Stated willingness of subject or Legally Authorized Representative (LAR) to comply with all study procedures and availability for the duration of the study
6. For females of reproductive potential: agreement to use highly effective contraception for during study participation. Highly effective contraception methods include:
 - Total abstinence (when this is in line with the preferred and usual lifestyle of the participant). Periodic abstinence (e.g., calendar, ovulation, symptothermal, post-ovulation methods) and withdrawal are not acceptable methods of contraception
 - Female sterilization (have had surgical bilateral oophorectomy with or without hysterectomy) or tubal ligation at least six weeks before taking study treatment.
 - Male sterilization (at least 6 months prior to screening). For female participants on the study the vasectomized male partner should be the sole partner for that participant.
 - Combination of the following (a+b or a+c, or b+c):
 - a. Use of oral, injected or implanted hormonal methods of contraception or other forms of hormonal contraception that have comparable efficacy (failure rate <1%), for example hormone vaginal ring or transdermal hormone contraception
 - b. Placement of an intrauterine device (IUD) or intrauterine system (IUS)
 - c. Barrier methods of contraception: Condom or Occlusive cap (diaphragm or cervical/vault caps) with spermicidal foam/gel/film/cream/vaginal suppository
7. For males of reproductive potential: use of condoms or other methods described above to ensure effective contraception with partner
8. Minimum body weight of 7.5 kilograms

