Following this initial dose titration phase, doses may be titrated at later weeks at the discretion of the PI, if there are concerns about safety, suboptimal efficacy, or if a subject has not yet achieved the target range of serum phosphate. To optimize serum phosphate levels throughout the dose cycle, Investigators may increase the dose of burosumab in 0.5 mg/kg increments in those subjects whose trough serum phosphate level (just prior to the next dose) is below the lower limit of the target range on 2 consecutive measurements performed at 4-week intervals (**Table 6**).

Table 6. Burosumab Dose Titration Scheme

Study Week	Serum Phosphate Level Z-score ¹	Dose Adjustment
Week 2	Less than -1	Increase the dose by 0.2 to 0.5 mg/kg at next dose
Week 2 6, 10 (adults)	> +2 ³	Decrease the dose by 0.2 to 0.5 mg/kg
Week 1, 2, 3 (pediatrics)		
Weeks 4, 8, 12, 16, 20, 24, 28, 32, 36, 40, 44	Less than -1 ²	Increase the dose by 0.2 to 0.5 mg/kg
	-1 to +2	Continue the current dose
	> +2 ³	Skip dose

¹ See **Table 5** for target phosphate levels according to age and sex-adjusted Z-scores

² If phosphate levels are below –1 standard deviation on 2 consecutive measurements, the burosumab dose may be increased by 0.5 mg/kg

³ If phosphate is Z-score > +2, withhold the next dose and reassess the serum phosphate level in 2 weeks. Once serum phosphate is in target range or less than Z-score –1, treatment may be restarted at 0.2 mg/kg less than prior administered dose. If more than 2 sequential phosphate measurements are > +2 Z-score range, the patient may be considered for study discontinuation.

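### The 8-week and total blood volumes in Section 8.2.2 do not appear to reflect the paediatric draw schedule, and the margin at the minimum weight is 3.75 mL

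*Combined protocol and SAP*

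**What the plan says.** Section 8.2.2 makes four linked statements about blood volume.

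- Study total: "The total amount of blood to be drawn over this study is 203 mL".
- Eight-week maximum: "The maximum amount drawn over an 8-week period is 67.5 mL".
- Children: at the minimum weight, "this corresponds to a maximum potential blood draw volume of 9 mL/kg over an 8-week period for pediatric patients". This is said to be below the Clinical Center limit of 9.5 mL/kg. The weight comes from Section 5.1: "Minimum body weight of 7.5 kilograms".
- Single day: "The maximum amount of blood drawn in a single day will not exceed 5 mL/kg for pediatric subjects".

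No volume is given for an NIH visit or for an outpatient draw, and nothing says whether outpatient draws are inside the 67.5 and 203 mL.

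The schedule requires serum outside NIH visits. Section 8.2 sends phosphate samples to local laboratories between visits. Footnote 6 of the Schedule of Activities says "Outpatient labs will be obtained 3 +/- 2 days and reviewed prior to burosumab administration". Table 6 in Section 6.1.2 lists phosphate checks every 4 weeks and, for children, the early entry "Week 1, 2, 3 (pediatrics". Section 4.1 has subjects evaluated weekly in Weeks 1 to 4.

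**The concern.** The stated total is almost exactly three times the stated 8-week maximum, and there are exactly three NIH visits (baseline, Week 24, Week 48). That is the pattern one would see if only NIH visits had been added up. A child also has outpatient serum draws, several of them close to baseline.

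The figure matters because it is a safety assurance for the smallest eligible children, tied explicitly to the minimum weight, and its margin is thin. If the 67.5 mL does not describe what a child's schedule requires, the stated 9 mL/kg is not the quantity that should be compared with 9.5 mL/kg.

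**Working it through.** **Plan's own figure.** 67.5 mL / 7.5 kg = 9.0 mL/kg. This reproduces.

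**Margin.** 9.5 mL/kg × 7.5 kg = 71.25 mL, and 71.25 − 67.5 = 3.75 mL.

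**Total against maximum.** 3 × 67.5 = 202.5 mL, which rounds to the stated 203 mL. With three equal NIH visits of 67.5 mL, about 0.5 mL is left for all outpatient draws together.

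**Draw count for a child (Table 6).** Weeks 1, 2, 3, 4, 8, 12, 16, 20, 28, 32, 36, 40 and 44 make 13 non-NIH draws; Week 24 is an NIH visit. Footnote 6 places the Week 8 draw 1 to 5 days before the dose, so Weeks 1, 2, 3, 4 and 8 give five draws in the first 56 days.

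**Can both figures include outpatient blood?** Let V be the volume of a follow-up NIH visit, d the extra volume at baseline, o the volume of one outpatient draw, n the number of outpatient draws and m the number in the first 8 weeks.

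- Maximum: V + d + m·o = 67.5
- Total: 3V + d + n·o = 203
- Subtracting the total from three times the maximum gives 2d = (n − 3m)·o − 0.5

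| Schedule assumed | n | m | Relation | Fits with o > 0 and d ≥ 0? |
|---|---|---|---|---|
| Child, Table 6 | 13 | 5 | d = −o − 0.25 | No |
| Adult, Table 6 (Weeks 2, 6, 10 plus 4-weekly) | 13 | 4 | o = 0.5 + 2d | Yes, e.g. d = 0, o = 0.5, V = 65.5 |
| 4-weekly plus Week 2 | 11 | 3 | o = d + 0.25 | Yes, e.g. d = 2, o = 2.25, V = 58.75 |
| 4-weekly only | 10 | 2 | o = (2d + 0.5)/4 | Yes, e.g. d = 4, o = 2.125, V = 59.25 |

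In the child row d must be negative, so follow-up NIH visits would have to draw more than baseline. If 203 is itself a rounded 202.5, the condition is d = −o, with the same conclusion. Footnote 5 of the Schedule of Activities points the other way, because it lists "intact FGF23 (baseline visit only), C-terminal FGF23 (baseline visit only), research blood": the two FGF23 assays add blood at baseline, not later.

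**Size if outpatient draws were omitted.** A child at 7.5 kg with five draws has (67.5 + 5o)/7.5 mL/kg. The limit is passed when o > 3.75/5 = 0.75 mL. The documents give no value of o, so the range below is an assumption.

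| o (mL) | 8-week volume (mL) | mL/kg at 7.5 kg | Weight at which it equals 9.5 mL/kg |
|---|---|---|---|
| 0.5 | 70.0 | 9.33 | 7.37 kg |
| 1 | 72.5 | 9.67 | 7.63 kg |
| 2 | 77.5 | 10.33 | 8.16 kg |
| 3 | 82.5 | 11.0 | 8.68 kg |
| 5 | 92.5 | 12.33 | 9.74 kg |

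With only Weeks 4 and 8 in the window, the break-even would be 3.75/2 = 1.875 mL per draw.

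**Size if another schedule was fully counted.** If the adult schedule was used, a child has one more draw in the window (5 against 4), and the limit is passed only when o > 3.75 mL. If a 4-weekly schedule was used, a child has three more draws, with break-even 3.75/3 = 1.25 mL. The table's example (o = 2.125) then gives 67.5 + 6.375 = 73.875 mL, or 9.85 mL/kg.

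**The case against.** Section 8.2.2 calls 67.5 mL the maximum drawn in 8 weeks, which on its face covers every draw. The division is correct, and no text says that outpatient blood is excluded. The near-match of 203 to 3 × 67.5 is not unique evidence of omission: the sparser and adult schedules in the table reproduce both figures with outpatient blood counted, and the baseline-only FGF23 assays make a larger baseline visit plausible. This stands, and omission cannot be asserted as fact.

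The early paediatric count can also be questioned. The Week −2 to 24 columns of the Schedule of Activities are not in the text available to me, so the count rests on Table 6. That is a titration table, and its Weeks 1, 2 and 3 entry sits beside the rule for phosphate above the target. Footnote 6 ties outpatient labs to dosing, and Weeks 1 and 3 are not dosing weeks in children. Section 4.1 supports weekly evaluation in Weeks 1 to 4 but does not mention blood. This lowers certainty about the count. It does not remove the point, because Table 6 cannot be applied at those weeks without a phosphate result.

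Three stronger readings are tempting, and the documents do not support them.

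- A reader might infer that small children will exceed the limit. That needs draw volumes the documents do not give.
- A reader might infer that 67.5 mL at one visit contradicts the single-day cap. It would be 9 mL/kg at 7.5 kg, and any child under 67.5/5 = 13.5 kg would need the draw spread over days. But Section 8.2.2 already commits to the cap, and visits may be inpatient, so this is not a contradiction.
- A reader might add screening blood taken under protocol 98-D-0145. The documents do not say whether it falls in the same 8 weeks or whether the limit sums across protocols.

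**Conclusion.** The 67.5 and 203 mL figures do not appear to describe the paediatric schedule. On the Table 6 schedule for children, with outpatient blood counted, they cannot both hold unless follow-up NIH visits draw more than baseline. They are consistent with outpatient draws having been left out, or with a sparser or adult schedule having been used; the documents do not settle which.

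Any breach of 9.5 mL/kg is conditional. At 7.5 kg it requires more than 0.75 mL per outpatient draw if these were omitted (five draws), or more than 3.75 mL if the adult schedule was fully counted. In the omission case, over assumed draws of 1 to 5 mL, it concerns children below about 7.6 to 9.7 kg. The conclusion rests on the Table 6 draw count and on a baseline visit at least as large as later ones. It is more than a missing detail, because a stated safety figure with a 3.75 mL margin seems to be computed for something other than the schedule it is meant to cover.

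**What to change.** In Section 8.2.2, recompute the 8-week maximum and the study total separately for the paediatric schedule, counting NIH visits and all scheduled outpatient draws. Show the volume per NIH visit and per outpatient draw so that the reader can see what each total includes, and restate the mL/kg at 7.5 kg.

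If the result stays below 9.5 mL/kg, the present assurance stands with its basis shown. If it exceeds 9.5 mL/kg, the draw volumes, the schedule and the minimum weight must be reconciled with the 8-week and 5 mL/kg single-day limits in the same section. How to do so is for the sponsor and the investigator.

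The cost is a recalculation and possibly a less favourable stated figure. No endpoint or analysis is affected.
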